5.2 EXCLUSION CRITERIA

- Age < 18 years old or > 75 years old;
- Non-shockable initial OHCA rhythm (pulseless electrical activity [PEA] or asystole);
- Valid do-not-attempt-resuscitation orders (DNAR);
- Blunt, penetrating, or burn-related injury, drowning, electrocution or known overdose;
- Known prisoners;
- Known pregnancy;
- Nursing home residents;
- Unavailability of the cardiac catheterization laboratory.
- Severe concomitant illness that drastically shortens life expectancy or increases risk of the procedure;
- Absolute contraindications to emergent coronary angiography
 - Known anaphylactic reaction to angiographic contrast media
 - Active gastrointestinal or internal bleeding

5.3 SCREEN FAILURES

Eligibility and exclusion criteria for ARREST are described in section 5.1 and 5.2 of this Protocol. Some of the criteria will not be ascertainable immediately following hospital arrival. These potentially include the age (18-75) in some cases, valid do-not-attempt-resuscitation (DNAR) orders, known pregnancy, absolute contraindications to emergent coronary angiography, and severe concomitant illnesses such as end-stage renal disease, end-stage liver disease, or stage IV cancer. Thus, some patients may be randomized and later found ineligible for the clinical trial. Their exclusion will be based on objective factors that are not related to the group to which they were randomized. We will record all required

information on such patients up to the point that their ineligibility is determined. Exclusion of these patients from the trial is unavoidable because some of the procedures to determine eligibility cannot be carried out immediately following hospital arrival. The intention-to-treat population will not include such screen failures. However we will retain all the information collected for such patients, including, especially, the reason(s) for exclusion, and will report on this population in tables presented to the Data and Safety Monitoring Board and in annual reports to NHLBI.

5.4 STRATEGIES FOR RECRUITMENT AND RETENTION

Enrollment is based on patients with refractory VF/VT out-of-hospital cardiac arrest treated by the EMS systems participating in the ongoing MRC Refractory VF/VT Protocol and transported to the University of Minnesota Medical Center, Fairview, where, immediately following hospital arrival, they will be evaluated by the research team for study inclusion and exclusion criteria and, if eligible, randomized and entered in the study.

Because the ARREST Trial will remain transparent to EMS providers, all patients receive the same CPR quality and treatment by the same EMS systems using ACLS guidelines and automated CPR (LUCAS™2), thus limiting potential confounders of differences in resuscitation care and CPR performance. Resuscitation interventions will be performed consistent with local practice and American Heart Association standards.³¹ If the patient has an initial cardiac arrest rhythm of VF/VT and continues to have VF/VT, antiarrhythmics may be administered per standard policy and procedure. If the patient does not develop ROSC after the first 3 defibrillation attempts and meets criteria for the University of Minnesota Refractory VF/VT Protocol (identical to the inclusion criteria for the ARREST Trial, but limited ARREST Trial exclusion criteria), paramedics call a central telephone number/dispatch per their standard practice. The research team will use the standard EMS call to mobilize and be present at the ED for the patient's arrival. MRC Refractory VF/VT Protocol patients are placed on LUCAS and are transferred to the University of Minnesota Medical Center, Fairview Hospital, with ongoing mechanical CPR per standard of care. Immediately following hospital arrival, the research team will evaluate the ARREST Trial inclusion and exclusion criteria and, if eligible, randomize and enter the patient in the study. Thus, paramedics are blinded to the study and out-of-hospital care is implemented using standard ACLS guidelines and automated CPR (LUCAS™2) for both groups.

The clinical CCL/ECMO team is always activated by the initial call and if not already in the hospital, it has a response time of 20 minutes from notification that happens at the time of EMS notification.

All entered study subjects or their legally authorized representative will have signed informed consent for continued participation in the trial and agreed to follow up assessment at 3 and 6 months. Contact information of the study subject, their significant other, and relevant additional contacts will be acquired prior to hospital discharge. Three and 6-month evaluations will occur by telephone or in-person during clinic appointments.

6 STUDY INTERVENTION

6.1 STUDY INTERVENTION(S) ADMINISTRATION

6.1.1 STUDY INTERVENTION DESCRIPTION

The ARREST study is a pragmatic clinical trial. Other than randomization to one of two arms [**Early ECMO Facilitated Resuscitation Arm** versus **Standard ACLS Resuscitation Arm**] there are no specified study interventions. All surviving patients will have their mRS and CPC score at hospital discharge determined; survival, mRS score, and CPC classification determined at 3 months post hospital discharge; and survival, mRS, and CPC classification determined at 6 months post hospital discharge. Cost per patient, cost per life saved (based on billing charges), safety and ECMO-related complications for the two treatment groups will also be determined.

Screening and Randomization.

There is no recruitment for this study as it is not possible to prospectively identify victims of out-of-hospital cardiac arrest. The subjects will be enrolled under exception from informed consent, 21 CFR 50.24.

EMS providers will deliver standard resuscitation procedures according to their standard practice. If the patient does not have ROSC following 3 defibrillations, EMS providers will call a central dispatch number per standard clinical practice, providing the research team with notification of a potentially eligible ARREST Trial study subject. At the same time the CCL/ECMO team is notified and activated. Immediately following hospital arrival, the research team will evaluate the ARREST Trial inclusion and exclusion criteria and, if eligible, randomize and enter the patient in the study, transferring the patient to the ED or CCL according to group allocation.

No Study Treatment; The following are suggested clinical practices that may or may not occur based on the judgment of the treating physician.

Early ECMO facilitated Resuscitation Arm. Following the standard EMS call to a central telephone number, if the research team determines the possible study subject would be randomized to the Early ECMO Facilitated Resuscitation Arm if entered in the study, they will begin mobilization of the CCL/ECMO team. EMS providers transport the patient to the University of Minnesota Medical Center, Fairview Hospital using the LUCAS device for CPR. Resuscitation interventions, including intravenous epinephrine, antiarrhythmics, defibrillation, and other appropriate treatments, occur prior to and during transport per EMS policy and procedure. Immediately following hospital arrival, the research team will evaluate the ARREST Trial inclusion and exclusion criteria and, if eligible, randomize and enter the patient in the study, directing the patient's hospital-based disposition. If the CCL/ECMO team is not in-house and has not yet arrived, resuscitation continues in the ED resuscitation area until arrival of the CCL/ECMO team. In this circumstance, given that average EMS transport times are 15 ± 5 minutes, it is expected that resuscitation will continue following arrival in the ED for about 10-15 minutes until CCL

personnel arrive. If the CCL is available the patient is directly transported to the CCL. Regardless of the presence of ROSC, ST-elevation myocardial infarction (STEMI) or acute ischemic changes on a 12 lead ECG, or VF/VT, PEA, or asystole cardiac arrest while in the ED, upon mobilization of CCL personnel, the patient is immediately transported to the CCL for coronary angiography and interventions, as appropriate. After arrival in the CCL, ongoing mechanical CPR continues, if required. The patient is immediately assessed on CCL arrival for resuscitation discontinuation criteria: 1) EtCO₂ upon arrival <10 mmHg, 2) PaO₂ < 50mmHg or O₂sat < 85%, and 3) serum lactate > 18mmol/liter. If the patient has > 1 criteria, resuscitation is terminated and the patient is declared dead. If the patient has 1 or no criteria, resuscitation efforts are continued. Emergency cannulation of the femoral vessels with a 15 or 17 french (Fr) arterial cannula based on size and gender and a 25 Fr venous cannula is performed with percutaneous technique and ultrasound (US) guidance. If there is difficulty in obtaining access or if the US suggests severe peripheral arterial disease, a descending aortic angiogram will be obtained to assess the ability of the femoral vessels to accommodate the size of the ECMO cannulas. In cases where the femoral vasculature cannot accommodate the ECMO cannulas, additional hemodynamic support is achieved by placement of an intra-aortic balloon pump (IABP) triggered by the aortic pressure generated by the LUCAS device. ECMO candidates are connected to the pre-primed CARDIOHELP circuit consisting of a centrifugal pump (Maquet Rotaflo; Maquet Cardiovascular; Wayne, NJ). Interventional cardiologists place all devices. Once hemodynamic/perfusion support is achieved, coronary angiography is performed and revascularization accomplished based on the clinical judgment of the interventional cardiologist.

Standard ACLS Resuscitation. If the patient is randomized to this protocol, research personnel will notify the ED MD about the randomization. Patients who have not achieved ROSC continue on ACLS resuscitation after arrival in the ED. Patients receive continued ACLS treatment in the ED for at least 15 minutes following ED arrival or at least 60 minutes from 911 call. If ROSC is achieved in the ED, the CCL team is mobilized and the patient transferred to the CCL per standard University of Minnesota clinical practice. If the patient has ROSC in the ED, but continues to re-arrest, the CCL team will not be mobilized until the patient demonstrates ROSC (as determined by the treating clinician, consistent with current clinical practice). If the ED MDs deem the ACLS effort futile at any point after 15 minutes of CPR from ED arrival or 60 minutes after the 911 if known, they can declare death.

Patients presenting or achieving ROSC in both group arms.

All patients with ROSC and pulses after VF/pVT OHCA gain access to the CCL per standard of care at the University of Minnesota. As such, those patients, in both groups will go to the CCL **regardless of arm allocation.**

VA ECMO or other circulatory support device initiation in those patients is based on the interventional cardiologist's clinical judgment. In general, evidence of the following are common indications for VA ECMO initiation in all CCL patients:

- i) Profound cardiogenic shock with SBP < 90 mmHg or MAP < 60mmHg despite inotropic support and an intra-aortic balloon pump,
- ii) Persistent hypoxia with arterial oxygen saturation < 90% despite maximum ventilatory support,

- iii) Florid pulmonary edema despite IV diuretics,
- iv) Recurrent episodes of VF or VT in the CCL.

Post-resuscitation Critical Care Recommended Pathway

Standard critical care measures follow guideline statements for post-cardiac arrest care^{13,17,18} and ECMO management¹⁹ with the following additional measures. All patients receive non-contrast computerized tomography (CT) scans of the head, chest, abdomen, and pelvis on CICU admission, assessing for cerebral anoxic injury, trauma, or bleeding. All patients receive therapeutic hypothermia (TH) for 24 hours. Goal temperature is 34° C, but is increased to 35-36° C if significant bleeding has occurred. Patients are maintained in 30-degree reverse trendelenburg with the head midline. Continuous electroencephalogram and near infrared spectroscopy (NIRS; Equanox; Nonin, Plymouth, MN) are initiated within 24 hours. NIRS measures cerebral oximetry and monitors brain perfusion while the patient is on ECMO. Hemodynamics are maintained with mechanical, inotrope, pressor, and vasodilator support to sustain a mean arterial pressure (MAP) between 65 and 100 mmHg. Fluid boluses provide euvolemic fluid status to prevent ECMO circuit chugging. ECMO flow is maximized until pressors are discontinued, then reduced, as tolerated, promoting native cardiac function. ECMO decannulation readiness is assessed daily with short durations of reduced ECMO flow and simultaneous echocardiography. On ECMO, ventilators are kept on rest settings with 7-10 cmH₂O positive end-expiratory pressure at 12 breaths per minute, and a tidal volume of 6-8 mL/kg ideal body weight. Plateau pressures are maintained below 30 cmH₂O. Settings are adjusted after ECMO decannulation. Continuous veno-venous hemodialysis is provided when needed. Potassium is replaced up to 3.0 mmol/L during TH and 4.0 mmol/L once rewarmed. Enteral nutrition is provided via oral-gastric (OG) or nasal-gastric (NG) access once rewarmed. All patients receive five days of empiric, broad-spectrum antibiotics with narrowed coverage thereafter, as necessary. Daily surveillance blood cultures are performed while on ECMO. Blood products are provided with a goal hemoglobin > 8 g/dL, platelets > 100,000 per μ L, and fibrinogen > 200 mg/dL. Heparin maintains an activated clotting time (ACT) of 180-200 sec while on ECMO. For life-threatening bleeding, the ACT goal is reduced as low as 140-160 sec. All PCI patients received aspirin 81mg and ticagrelor by NG or OG tube.⁵⁹

ECMO Exposure. Patients in both groups receiving ECMO are anticipated to require ECMO support for a longer duration than 6 hours and are expected to be in the range of 3 - 5 days or longer.

The expected duration of ECMO support is based on the investigators' experience implementing the MRC Refractory VF/VT Protocol (J Am Coll Cardiol. 2017 Aug 29;70(9):1109-1117). From December 1st, 2015 through February 29th, 2017, 62 patients met MRC Refractory VF/VT Protocol criteria for EMS transport. Left ventricular function was severely compromised for the first 48 hours in all patients admitted to the intensive care unit (ICU), but significant recovery was observed within 5 days. An intra-aortic balloon pump was inserted in 25 (45%) of 55 patients. The mean left ventricular ejection fraction in survivors was 18 \pm 19% at 24 hours, 34 \pm 19% at 48 hours, 43% \pm 16% at 5 days, and 48% \pm 11% at hospital discharge. After CCL treatment, extracorporeal life support (ECLS) was continued for 3.0 \pm 2.0 days.

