4 STUDY DESIGN

4.1 OVERALL DESIGN

Primary Hypothesis.

Based on the promising preliminary experience, we hypothesize that the Early ECMO Facilitated Resuscitation Arm will facilitate the identification and treatment of reversible CAD and significantly improve survival to hospital discharge compared with the Standard ACLS Resuscitation Arm.

Phase of the trial.

This is a Phase II, single center, partially blinded, prospective, intention to treat, safety and efficacy clinical trial.

Measures to Minimize Bias.

- Initial patients will be randomly allocated to one of the 2 regional standards of care in a 1:1 ratio. According to the University of Minnesota Refractory VF/VT Protocol, EMS providers always use a central telephone number to notify that a refractory VF/VT patient is being transported. The research team will use this standard EMS call to mobilize and be present at the ED for the patient's arrival. Immediately following hospital arrival, the research team will evaluate study entry criteria and, if eligible, randomize and enter the patient in the study, transferring the patient to the ED or CCL. In this way, the study will remain completely transparent to EMS providers, eliminating potential bias in EMS treatment pre arrival. It is impossible to blind treatment assignment in the CCL, but the study has been designed to eliminate bias in the out-of-hospital setting. Emergency department and CCL personnel will be aware of group assignment, but treatments will follow the current clinical standards of care. Post CCL care providers for patients admitted to the coronary intensive care unit (CICU), from both arms, will be instructed to not seek information about group assignment unless, in their judgment, a medical situation of critical clinical importance requires it.
- All patients will be treated with the same established CICU post-arrest protocols established by the Center for Resuscitation Medicine.
- Patients in the Early ECMO Facilitated Resuscitation Protocol Arm can also be held for a few minutes in the ED until the CCL team arrives during which time they will receive continued ACLS. That fact makes the distinction between arms by hospital providers very difficult when patients are admitted.

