6.3 MEASURES TO MINIMIZE BIAS: RANDOMIZATION AND BLINDING

Patients eligible for this study will be VT/VF OHCA patients refractory to standard treatment as defined by the ARREST Trial inclusion and exclusion criteria. Initially patients will be randomly allocated in a 1:1 ratio immediately following hospital arrival. As noted in the Statistical Considerations section, this trial has a Bayesian Adaptive Design, which means that the treatment allocation ratio may be changed later to reduce the probability of assignment to an inferior treatment arm. See Section 9 below. The study has been designed to minimize treatment bias as far as possible. EMS providers will be blinded to the study. University of Minnesota Refractory VF/VT Protocol patients are placed on LUCAS and transferred to the University of Minnesota with ongoing mechanical CPR per standard of care. All out-of-hospital care, including CPR, ACLS, and resuscitation efforts, will be implemented using ACLS guidelines and automated CPR (LUCAS™2) and treatment will be unchanged. Patients will be randomized and entered in the study by research personnel only after hospital arrival and assessment of ARREST Trial inclusion and exclusion criteria. Emergency department personnel will be aware of group assignment. However, ED treatment of all patients follows protocol and standard of care. CCL personnel also will be aware of group assignment, but treatment is similarly protocolized. Post-CCL care in the CICU will be blinded to group assignment. Patients in both groups could have received identical treatment. Patients from both groups will be treated with the same established CICU post arrest protocol by the same critical care team. The PIs will not be involved in any end-of-life decision making. The **Figure** below shows the phases of care in which providers are blinded to group allocation (in light blue).

Thus, we expect patients in both groups to similarly reflect the gender, ethnic diversity, severity or duration of cardiac arrest, and receive the same therapy except early ECMO facilitated resuscitation versus standard ACLS resuscitation.

[figure not shown]

Figure: Patient flow chart showing blinding.

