APPENDIX A: EFIC PLAN

Advanced R²Eperfusion STRategies for Refractory Cardiac Arrest (The ARREST Trial)

Waiver of Informed Consent Requirements in certain Emergency Research

Plan for fulfillment of the requirements of 21 CFR 50.24

INTRODUCTION

The goal of this document is to provide a logistical outline for the implementation of the additional protections associated with 21 CFR 50.24, Waiver from Informed Consent Requirements for Emergency Research as related to the ARREST study. The implementation of this plan is the first phase of conducting the proposed trial and the data acquired from the planned activities will be presented to the IRB to assist in the deliberations regarding the approval process for the study to take place. Additional resources may be requested to assist in review of this plan and are available from the Principal Investigator, [name] MD.

Refractory VF/VT is a spectrum of timing of return of spontaneous circulation (pulses) in response to standard ACLS treatment ranging from return of pulses shortly after the third failed shock (as defined in this protocol) to never. In any individual case, it is impossible to determine where along this continuum the patient may ultimately fall. For patients who will never obtain a pulse, science supports the contention that the sooner ECMO is initiated the potentially better the outcome.^{11, 37, 40, 41, 44, 59, 60} In order to achieve early administration of ECMO from OHCA, it is necessary to begin mobilization from the scene to the hospital immediately following the third failed shock and enter the patient in the study immediately after determination of eligibility and randomization following hospital arrival.³⁹ Accordingly, science supports the definition of a therapeutic window for this study as initiation of the study intervention (e.g. implementation of one of two standards of care) as soon as possible.^{11, 37, 39, 40, 41, 44, 59, 60} For patients who will never obtain a pulse, even several minutes delay may make the difference between an outcome of life or death.

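### Section 6.1.1 lets the research team look up the arm before it judges eligibility, against the plan's own stated order; separately, Sections 5.3 and 9.3 drop randomised patients without requiring that the reason predate randomisation

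*Combined protocol and SAP*

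**What the plan says.** **Order of events.** Section 4.1: "Immediately following hospital arrival, the research team will evaluate study entry criteria and, if eligible, randomize and enter the patient in the study". Section 6.3 says patients are randomised "by research personnel only after hospital arrival and assessment of ARREST Trial inclusion and exclusion criteria". Appendix A agrees: "enter the patient in the study immediately after determination of eligibility and randomization following hospital arrival". The Early ECMO arm paragraph of Section 6.1.1 says the same in its later part: "if eligible, randomize and enter the patient in the study, directing" the patient's disposition. Earlier in that paragraph, between the EMS call and arrival, mobilisation of the cath-lab/ECMO team begins "if the research team determines the possible study subject would be randomized to the Early ECMO Facilitated Resuscitation Arm if entered in the study". Section 9.1 also still describes the ECMO group as randomised in the field.

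**Team activation.** Section 5.4: "The clinical CCL/ECMO team is always activated by the initial call". Section 6.1.1, Screening and Randomization: "At the same time the CCL/ECMO team is notified and activated". Section 6.1.1, Standard ACLS: "If ROSC is achieved in the ED, the CCL team is mobilized".

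**Exclusion after randomisation.** Section 5.3 recognises that some criteria cannot be checked on arrival. Randomised patients later found ineligible leave the intention-to-treat population. The plan says this will rest on objective grounds unconnected with the assigned arm. Required information is recorded only until ineligibility is established, and the group is tabulated for the DSMB and in annual reports to NHLBI. Section 9.3 limits such exclusion to prespecified criteria. The only other analysis population it defines is as-treated.

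**The concern.** **(A) Early sight of the arm.** If the look-up were carried out as written, the people deciding who enters would already know the next assignment. Some criteria leave room for judgement: Section 5.2 excludes severe concomitant illness that shortens life expectancy or raises procedural risk. Knowing the arm before applying such a criterion is what concealment is meant to prevent.

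**(B) Late exclusion.** Dropping a randomised patient is defensible when the reason existed before randomisation and is judged without regard to arm or outcome. The plan asserts independence from arm but does not tie the fact to a time. Section 5.3 lists absolute contraindications to angiography among the things that may be found late, and Section 5.2 counts active internal or gastrointestinal bleeding among them. Bleeding can begin after randomisation; Section 8.3.3.3 lists transfusion-requiring bleeding as potentially related to reperfusion strategies. It may also be detected differently by arm. Early-ECMO patients go to the cath lab regardless of ROSC, whereas standard-arm patients without ROSC may be declared dead in the ED, and the CT scan for bleeding comes at CICU admission. Because data are required only up to ineligibility, discharge survival may be missing for those alive when excluded. The primary result could then not be fully checked on all randomised patients.

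**Working it through.** **Part (A): the texts side by side.** No arithmetic applies.

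1. Section 4.1, Section 6.3, Appendix A, the Screening text of 6.1.1 and the later part of the Early ECMO paragraph give the order: arrival, eligibility, randomisation.
2. One sentence gives: EMS call, arm determined, team mobilised if ECMO, arrival, eligibility.
3. The stated purpose of the look-up is mobilisation. Sections 5.4 and 6.1.1 (Screening) already activate the team on every call, so on those texts the look-up serves no purpose.
4. The Standard ACLS text ties mobilisation to ROSC. That may mean a later step than activation, but the terms are not defined.

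**Part (B): an illustration.** Inputs from Section 9.1: Beta(1,1) priors; looks at 30, 60, 90, 120 and 150 evaluable patients; threshold 0.986 in both directions; 1:1 for the first 30, then allocation probability equal to the posterior probability, limited to 0.25–0.75 (the 3:1 cap). There were 200,000 simulated trials per scenario; the Monte Carlo standard error is about 0.0004 near 0.03.

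Check against the plan's own table:

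| Quantity | Plan | Simulation |
|---|---|---|
| Null rejection (0.12 vs 0.12) | 0.048 | 0.0487 |
| Power (0.37 vs 0.12) | 0.905 | 0.902 |
| Mean N, null | 148.5 | 147.0 |
| Mean N, alternative | 81.6 | 82.6 |

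The match is close but not exact.

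If a fraction x of an arm with true survival 0.12 is removed, all of them non-survivors, survival among those analysed is 0.12/(1 − x): 0.126, 0.133 and 0.141 for x = 5, 10 and 15%. With no true effect:

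| Removed, ECMO / standard | False superiority | False inferiority |
|---|---|---|
| 0 / 0 | 0.0246 | 0.0241 |
| 5% / 0 | 0.0309 | 0.0202 |
| 10% / 0 | 0.0391 | 0.0163 |
| 15% / 0 | 0.0502 | 0.0134 |
| 0 / 5% | 0.0207 | 0.0305 |
| 0 / 10% | 0.0169 | 0.0394 |
| 0 / 15% | 0.0133 | 0.0506 |
| 10% / 5% | 0.0316 | 0.0207 |
| 15% / 10% | 0.0344 | 0.0214 |
| 5% / 5% | 0.0259 | same by symmetry |
| 10% / 10% | 0.0264 | same by symmetry |
| 15% / 15% | 0.0277 | same by symmetry |

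Total rejection for one-arm ECMO removal is 0.0511, 0.0554 and 0.0636.

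**Scale.** With about 74 analysed per arm (the plan's null average), the removals number 74x/(1 − x) = 3.9, 8.2 and 13.1 patients. The plan allows 175 − 150 = 25 (Section 9.1) or 174 − 148 = 26 (Section 9.2) patients. Section 9.2 says its allowance covers both withdrawal and false-positive randomisations, without a split. The largest case therefore uses 13.1/25 = 52% of it.

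**The case against.** On (A), the sentence stands under a line in Section 6.1.1 that calls what follows suggested clinical practices that may or may not occur. Section 6.3, which governs randomisation, is categorical the other way. Paramedics are blinded to the study and, under Section 5.4, refer on criteria identical to the trial's inclusion criteria, so mainly the exclusion criteria are exposed. All of this stands. A reader might infer that concealment was actually lost; the documents do not show that. They show one sentence that contradicts the rest.

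On (B), the wording of 5.3 and 9.3 and most of the listed examples describe late discovery of baseline facts. The grounds are stated to be objective and unconnected with arm, the criteria are prespecified, and the exclusions are disclosed to the DSMB and NHLBI. These are real safeguards, and they narrow the point to a missing time anchor and missing data. A reader might infer that the exclusions bias the trial towards ECMO or inflate its type I error. The documents give neither the number, the arm split nor the outcomes of excluded patients, and the larger figures above need all removals to be non-survivors from one arm. A reader might also borrow the 45% pathway survival in Section 2.1 to argue a power loss. That figure describes patients treated under the pathway, not patients later found ineligible, and gives no basis for it.

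**Conclusion.** (A) is wrong as written: a contradiction within the plan that would break concealment if followed, probably a drafting remnant like the field-randomisation phrase in Section 9.1. (B) is a prespecified, disclosed modification of intention-to-treat that lacks three things: a rule that the excluding fact predate randomisation, discharge survival for those excluded, and an analysis of everyone randomised. Reporting of exclusions by arm is not stated either.

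The effect of (B) cannot be derived from the documents. Under assumed exclusion rates it is small to moderate, can run in either direction, and nearly vanishes when removals are balanced. Partly balanced removals give false superiority of about 0.032–0.034 against about 0.025. The case for change rests on the text and the low cost, not on these illustrations. Worth fixing, with medium confidence.

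**What to change.** **(A)** Delete the pre-arrival arm look-up in Section 6.1.1 and state that the arm is released only after eligibility has been recorded. Reconcile the activation and mobilisation wording in Sections 5.4 and 6.1.1 (Screening, Early ECMO and Standard ACLS texts), and the field-randomisation phrase in Section 9.1. Which activation practice applies is for the sponsor to settle, provided it does not depend on knowing the arm before eligibility is recorded. Cost: wording only.

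**(B)** In Sections 5.3 and 9.3, limit exclusion after randomisation to prespecified facts that existed before randomisation. Record survival to hospital discharge for every randomised patient as far as consent and withdrawal rules allow. Report exclusions and reasons by arm, and add a sensitivity analysis of the primary endpoint on all randomised patients.

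Cost: minor extra data collection, one table and one analysis. The analysis may stay incomplete where continued participation is refused, since Section 10.1.1 requires written consent before study procedures continue. A few ineligible patients may also remain in the primary set.
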